3.1.1 Selection of the Recommended Phase 2 dose

Selection of the RP2D and schedule for SL-172154 monotherapy will be based upon the totality of the data in subjects treated in dose escalation, dose expansion and pharmacodynamic cohorts. Approximately 6-12 subjects (inclusive of the subjects enrolled at this dose in the Dose Escalation, Pharmacodynamic cohort, and Dose Expansion) may be treated at the RP2D.

3.1.2 Sample Size

If only Schedule 1 is evaluated, the planned total sample size is 21 for dose escalation. If Schedule 1 and Schedule 2 are both fully evaluated in dose escalation, the maximum planned sample size for dose escalation is 42 This sample size assumes evaluation of approximately 21 subjects across 5 dose levels in dose escalation on Schedule 1 and 21 subjects across 5 dose levels on Schedule 2. Approximately 6 subjects may be enrolled in an optional pharmacodynamic cohort. After a dose and schedule are selected, approximately 6 subjects will be included in the dose expansion cohort. The number of subjects in dose expansion will vary depending on the number of subjects enrolled in both the dose escalation and pharmacodynamic cohorts at a potential RP2D. The goal is to enroll approximately 6-12 subjects at the potential RP2D, including subjects in the dose escalation, pharmacodynamic, and dose expansion cohorts. Overall, the total sample size estimate for this study is 33 subjects assuming only Schedule 1 is evaluated, and 54 subjects if both Schedule 1 and Schedule 2 are fully evaluated. See Section 9.1 for more details.

3.2 Justification for Starting Dose and Schedule of SL-172154

Analysis of available data support a starting dose of 0.1 mg/kg for the administration of SL-172154 to humans via IV infusion. The starting dose for the FIH clinical study of SL-172154 was determined based on MABEL principles, taking into account available preclinical pharmacology, toxicology, and pharmacokinetic data. The most sensitive in vitro measure of biological activity in response to SL-172154 exposure was the PBMC proliferation assay conducted in AIMV medium. Additional key data to support selection of the starting dose for the FIH study is data from cynomolgus monkey toxicology studies, including identifying the NOAEL, and the pharmacokinetic results.

The *in vitro* potency of SL-172154 in human PBMCs was estimated using the AIMV (Alstroemeria-Mosaic Virus) proliferation assay. PBMCs from humans and cynomolgus monkeys (9 donors/species) were exposed to increasing concentrations of SL-172154 (0 to 100 nM) for 7 days after which absorbance of each sample was measured at 490 nm as an index of cell proliferation. This study demonstrated a dose-dependent increase in proliferation in both humans and cynomolgus monkeys PBMCs. While human PBMCs were overall more sensitive, there was similarity in the degree of SL-172154-stimulated proliferation in humans and cynomolgus monkeys at both EC_{20} and EC_{50} . An EC_{20} value of 5.18 nM was calculated for human PBMC proliferation using a baseline Emax model. The human EC_{20} has been chosen as the target Cmax concentration benchmark for systemic exposure, consistent with the conclusion by Saber et al. that a starting dose of 10 to 30% pharmacologic activity was acceptable for CD3 targeted bispecific constructs [Saber, 2017].

In vivo monkey PK data from the GLP toxicology study [Report_SL2020IB001] were used to convert the target Cmax to a human equivalent dose (HED). In the monkey GLP toxicology study, a dose of 1 mg/kg was associated with a mean Cmax of 1230 ng/mL (13.96 nM, n=6 monkeys). Note that the lowest dose studied in the GLP study was 0.1 mg/kg; however, the Cmax was not well characterized as only two animals had measurable concentrations at this dose level. The non-quantifiable concentrations were likely due to the rapid clearance of SL-172154 from the serum. Potential explanations for rapid drug clearance include an antigen sink due to the ubiquitous expression of CD47 on peripheral blood cells (i.e., RBC, platelets, PBMC) and target-mediated uptake at early time points with trafficking of cells (e.g., PBMC) and bound drug to peripheral tissues. From Day 15 onwards, the removal of drug by anti-drug antibodies results in rapid

CONFIDENTIAL Compound: SL-172154

clearance. Assuming dose-proportionality, a dose of 0.4 mg/kg in the monkey is predicted to achieve the preliminary human target Cmax (5.18 nM). The 0.4 mg/kg dose level in monkeys was converted to a HED using a standard conversion factor of 0.32 [FDA, 2005]. The resultant preliminary starting dose for IV infusion of SL-172154 in humans is 0.1 mg/kg (0.4 mg/kg x 0.32).

The GLP study concluded that 1.0 mg/kg was considered to be NOAEL for IV infusion doses of SL-172154. Thus, the proposed SL-172154 starting dose of 0.1 mg/kg is 1/10th the NOAEL dose of 1 mg/kg observed in cynomolgus monkeys and provides an appropriate safety margin for the FIH starting dose.

Justification for Schedule: A weekly dosing schedule for 5 consecutive weeks was implemented in the NHP studies. Toxicity was dose-dependent (only at the higher doses) and occurred at the third and subsequent doses. Receptor occupancy data from Day 1 (Dose 1) demonstrated that SL-172154 readily bound to its intended target in a dose-dependent manner, attaining >90% CD40 receptor occupancy on PBMCs and ~80% CD47 receptor occupancy on RBCs in the 10 and 40 mg/kg groups. Maximal occupancy for the CD47 receptor on RBCs was attained by 1 hour postinfusion and persisted through at least 168 hours. CD40 receptor occupancy was transient, likely influenced by endocytosis and migration of CD40+ cells to tissues including the spleen.

Based upon the durability of binding for SL-172154 to CD47, dosing for the clinical trial will begin by incorporating administration of SL-172154 on Schedule 1 on Day 1, 8, 15, and then every 2 weeks thereafter. The Day 8 dose was retained as no toxicity was observed at this time point, minimal pharmacodynamic effects were noted, and this dose may have contributed to the pharmacodynamic effect on day 15. In NHPs, multiple factors may have contributed to the onset of reactions at Day 15 including ADA, complement activation, margination of lymphocytes and cytokine elevations. It is unknown if these contributing factors would be observed in humans at the doses studied. Therefore, dosing on Day 1, 8, 15 is considered acceptable. The 2-week treatment free interval beyond Day 15 may allow for pharmacodynamic effects to subside between subsequent doses and to mitigate toxicity. A more or less intensive dosing schedule may be instituted if safety and pharmacodynamic data support more or less frequent dosing of SL-172154 (e.g., one dose given weekly on Schedule 2 or every two weeks or every 3 weeks or every 4 weeks).

3.2.1 Criteria for Decision to Transition from Schedule 1 to Schedule 2

Schedule 1 may be safe and tolerable, but pharmacodynamic effects may not be present or detectable, or pharmacokinetic parameters may suggest that a more frequent dosing schedule is warranted. In this event an alternative dosing schedule (i.e., Schedule 2; once weekly dosing over 28 days in each cycle) will be explored in lieu of Schedule 1. During dose escalation pharmacokinetic parameters will be analyzed by dose level and subjects will be monitored for pharmacodynamic effects pre- and post-dose. Dynamic changes that are anticipated following administration of pharmacologically active doses of SL-172154 include:

- Changes from baseline in cell counts and percentages of circulating immune cells including T cell subsets, B cell subsets, and myeloid cells
- Increase in cytokines/chemokines
- Changes in circulating immunoglobulins

- Free/Total receptor occupancy of CD47 and CD40
- Appearance of activation markers on the surface of CD4 lymphocytes and macrophages in the peripheral blood

The anticipated timing of pharmacodynamic effects based on NHP studies is at cycle 1, day 15 (C1D15) and beyond, although these effects may be observed as early as C1D1 and C1D8.

3.3 SL-172154 Dose Escalation Plan

Dose escalation will begin on Schedule 1 at the starting dose of 0.1 milligrams per kilogram (mg/kg) as outlined in Table 1 below. Intermediate or higher dose levels not shown may be explored based on emerging data (e.g., safety and pharmacodynamic data). Dose escalation of SL-172154 will not exceed half-log increments. The DLT assessment period is 28 days in length and ends 14 days after the last dose is administered in the first cycle on Schedule 1 and 7 days after the last dose is administered on Schedule 2. Dose escalation will follow the mTPI-2 decision rules outlined in Table 7 in Section 9.1.

- Schedule 1 administration for SL-172154: Given on days 1, 8, and 15 in cycle 1 over 28 days and then every two weeks thereafter on days 1 and day 15 in cycles \geq 2 every 28 days.
- Schedule 2 administration for SL-172154: Given on days 1, 8, 15 and 22 of each 28-day cycle
- Cycle length for Schedules 1 and 2: 28 days
- **DLT assessment period for Schedules 1 and 2**: 28 days

Table 1: SL-172154 Dose Escalation Plan in Phase 1
--

	Dose LevelIV Dose of SL-172154 (mg/kg) ^{a,b,c,d,e} Duration of Infusion ^d				
Lev	evel 1 - starting dose 0.1 30 minutes (+/- 10 minutes)				
Lev	vel 2	0.3	30 minutes (+/- 10 minutes)		
Lev	vel 3	1.0	30 minutes(+/- 10 minutes)		
Level 4 3.0 60 minutes (+/- 15 minutes)					
Level 5 10.0 60 minutes (+/- 15 minutes)					
a) b)	cycle 1 and then on days Dose escalation on Sched once weekly on days 1, 8	1 and 15 in cycles \geq 2. Jule 2 may be tested: If Schedule 2 is of , 15, and 22 of each 28-day cycle.	in 28-day cycles on days 1, 8, and 15 in pened, SL-172154 may be administered		
c) d)	kg. For subjects with body weight >100 kg, the dose to be administered should be the same as that calculated for a subject weighing 100 kg (see Section $5.1.4$).				
e)	Infusion time may change based on final drug volume needed for administration, safety and tolerability of the infusion for the subject and/or observed safety findings during the study. Please refer to the Study				

Pharmacy Manual (SPM) for details.

Evaluation of an Alternative Dosing Schedule: Safety, pharmacokinetic and/or pharmacodynamic data from the dose escalation cohorts and pharmacodynamic cohorts, if available, may support exploration of a more or less intensive dosing schedule for SL-172154. If these data from Schedule 1 support exploration of more frequent dosing (see Section 3.2.1 for criteria needed to transition to Schedule 2), then cohort enrollment on Schedule 2 will be instituted in lieu of Schedule 1. The starting dose on Schedule 2 will be at a dose level that has completed evaluation for safety on Schedule 1 as defined by the mTPI-2 design. Dose escalation (or de-escalation) may then proceed on schedule 2 as shown in Table 1. During dosing on Schedule 2, SL-172154 will be administered once weekly (D1, D8, D15, and D22) every 28 days. If less frequent dosing is supported by safety, pharmacokinetic and/or pharmacodynamic data, SL-172154 may be administered once every two weeks, once every three weeks or once every four weeks. The starting dose on a less frequent schedule would be instituted at a dose level that has completed evaluation for safety as defined by the mTPI-2 design, emerging safety data and as recommended by the SMC.

3.3.1 Intrasubject Dose Escalation

Intrasubject dose escalation(s) may be considered on a case-by-case basis, provided that the subject has completed at least 2 cycles at the originally assigned dose, has tolerated treatment well, and experienced \leq Grade 1 toxicity on the most recent cycle of SL-172154 therapy. A subject's dose may be increased to a dose level that has completed evaluation for safety and has not exceeded the MTD. Approval for intrasubject dose escalation must be obtained from the Sponsor Medical Monitor and must be documented on an Intrasubject Dose Escalation Decision Form provided by the Sponsor.

3.4 Definition of Dose-Limiting Toxicity

DLTs are as defined in the bulleted points below. Toxicities will be graded as per National Cancer Institute Common Terminology Criteria for Adverse Events version 5 (NCI CTCAE v5). The determinate period for DLT is the first 28 days of SL-172154 dosing on Schedule 1 or Schedule 2. **Note**: AEs clearly related to disease progression or intercurrent illness are not considered DLTs. Inflammatory reactions attributable to local anti-tumor responses (e.g., severe pain) are not considered DLTs.

- Any death not clearly related to underlying disease or extraneous causes
- Any \geq Grade 4 AE
- Elevations in liver transaminases (aspartate aminotransferase [AST], alanine aminotransferase [ALT]) and/or total bilirubin:
 - In subjects who enroll with AST/ALT/total bilirubin \leq upper limit of normal (ULN); AST or ALT elevation of >8 x ULN or total bilirubin > 5 x ULN
 - In subjects who enroll with AST/ALT/total bilirubin > ULN; AST or ALT elevation of >8 x baseline or total bilirubin > 5 x baseline
 - Evidence of Hy's Law (AST or ALT > 3 x ULN [or baseline*] with concurrent increase in total bilirubin > 2 x ULN [or baseline*] without evidence of cholestasis or alternative explanation such as disease progression or viral hepatitis; *ULN or baseline dependent on value at enrollment as described above.
- Any AE that requires permanent discontinuation of SL-172154
- Any Grade 3 or greater AE except for those listed below:
 - \circ Grade 3 fatigue lasting \leq 7 days
 - Grade 3 anemia
 - Grade 3 or 4 neutropenia not associated with fever that improves to Grade 2 within 7 days.
 - Grade 3 or 4 lymphopenia
 - Grade 3 thrombocytopenia not associated with clinically significant bleeding and does not require medical intervention
 - Grade 3 electrolyte abnormalities that are not associated with clinical signs/symptoms and are reversed with appropriate medical intervention
 - Grade 3 laboratory abnormalities that are not deemed clinically significant by the SMC.
 - Indirect/unconjugated hyperbilirubinemia without significant clinical consequences
 - Grade 3 or 4 amylase and/or lipase abnormalities that are not associated with clinical signs/symptoms or findings on imaging consistent with pancreatitis
 - Grade 3 vomiting and/or Grade 3 nausea that resolves within 72 hours with appropriate clinical management
 - Grade 3 hypertension that can be controlled (i.e., systolic BP < 140 mmHg and diastolic BP < 90 mmHg) with medical therapy.
 - Grade 3 endocrine disorder (thyroid, pituitary, hyperglycemia and/or adrenal insufficiency) that is managed with treatment with resolution of symptoms within 14 days after treatment onset.
 - Grade 3 diarrhea with no evidence of colitis that resolves within 72 hours with appropriate clinical management
 - Vitiligo or alopecia of any grade
- Other AEs may be considered a DLT as determined by the investigator in conjunction with the SMC.

A Grade \geq 3 AE(s) that occurs beyond the DLT period or Grade 2 events that require continuous interruption of SL-172154 for more than 6 weeks or AEs that result in subjects not receiving at least 2 of the 3 scheduled doses of SL-172154 on Schedule 1 (or at least 2 of the 4 scheduled doses of SL-172154 on Schedule 2) during the DLT assessment period due to AE(s) may be taken into consideration when assessing the totality of the data in determining DLT and the RP2D.

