In the GLP study, the occurrence of dose-dependent infusion-related reactions (IRRs) at 10 and 40 mg/kg (Days 15 or 22) resulted in early termination of dosing in these two dose groups with 2 monkeys in the 40 mg/kg group euthanized in extremis [a female on Day 15 (Dose 3) and a male on Day 22 (Dose 4)]. Minimally to moderately decreased platelets occurred at ≥10 mg/kg (Days 16 and 23) and transient, mild decreases in lymphocytes were seen in the 40 mg/kg group (both sexes on Days 2 and 16; 2 of 4 males on Day 23). Dose-dependent increases in splenic weight and increased lymphoid cellularity in the spleen and lymph node were noted and attributed to SL-172154 administration. These findings were reversed after a 4-week recovery period. Assessment of pharmacodynamic biomarkers showed that SL-172154 occupied CD40 and CD47 receptors on circulating blood cells and caused elevations in a number of serum cytokines. Transient and reversible complement activation was coincident with the production of ADA to SL-172154. Additionally, the presence of ADA from at least Day 15 (Dose 3) onward likely contributed to low or non-quantifiable plasma SL-172154 concentrations on Day 29. At the 1.0 mg/kg dose level, there were no clinical observations, abnormalities in clinical pathology parameters, or non-reversible pathology findings, thus 1.0 mg/kg was considered to be the no-observed-adverseeffect level (NOAEL) for intravenous infusion doses of SL-172154. The 1.0 mg/kg dose corresponded with mean Cmax and AUC_{0-last} values of 1230 ng/mL and 518 ng*h/mL on Day 1. The mean terminal elimination half-life $(t^{1/2})$ on Day 1 was approximately 0.4 hours following a 1 mg/kg dose and was higher with mean values of approximately 1.1 and 0.9 hours for the 10 mg/kg and 40 mg/kg dose groups, respectively.

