6.1.2 Correlative Sample Time points for SL-172154

Table 6: Complement, Immunophenotyping, Receptor Occupancy Time Points

	C1/D1 and C2/D1	id C2/D1	C1/D2 and C2/D2	C1/D3	C1/D15 a	C1/D15 and C2/D15	C1/D16 and C2/D16
Samples	Predose (-90 to -5 min)	1hr post EOI (±10 min)	24 hr post EOI (± 2hr)	48 hr post EOI (± 2hr)	Predose (-90 to -5 min)	1hr post EOI (±10 min)	24 hr post EOI (± 2hr)
Complement (SC5b-9) ^{1,2}	X ² (C1/D1 only)	X ² (C1/D1 only)			X ² (C1/D15 only)	X ² (C1/D15 only)	
Immunophenotyping ¹	X	X	X	X	X	X	X
Receptor Occupancy ¹	X	X	X	X	X	X	X
		Date	and clock time for sal	mple collection (pr	e/post dose) will be r	bate and clock time for sample collection (pre/post dose) will be recorded for all samples	S
1. Refer to SLM for details	tails						

Complement is collected at predose and 1 hr post EOI time points on days 1 and 15 in cycle 1 only. 1 1

79

CON	CONFIDENTIAL																		SL0:	SL03-OHD-101	-101
Com	Compound: SL-172154																		Vers	Version no: 6.0	6.0
Dos	Dosing Schedule 2							D1,]	D8, D15	, D22 o	D1, D8, D15, D22 over 28 days in each cycle	lays in	each cy	cle							-
Cyc	Cycle Length = 28 days					Cycle 1						Cycle 2	e 2				Cycle ≥ 3	> 3		Post	
		Screen ^a	D1	D2	D3	D8	D15	D16	D22	D1	D2	D8	D15	D16	D22	D1	D8	D15	D22	TXT	F/U ^u
Pro	Procedures/ Assessments ^b Study Days	Days -21 to -1	1	2	3	8	15	16	22	29	30	36	43	44	50	57 etc.	64 etc.	71 etc.	78 etc.	w/in 30 d	Off TXT
HRI	HRD Status ^s	X																			
Surv	Survival																			X	X

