4. ANALYSIS POPULATIONS

Population	Description
Screened	All subjects who have signed the main study inform consent form.
Screen Failures	All subjects who have signed the informed consent but have not received any dose of SL-172154.
All Treated	All subjects who receive at least one dose of SL-172154. Safety data will be evaluated based on this population.
DLT Evaluable	All subjects enrolled in the dose escalation cohorts 1) who have received ≥ 2 of the 3 scheduled doses of SL-172154 on Schedule 1 or who have received ≥ 2 of the 4 scheduled dose of SL-172154 on Schedule 2 during cycle 1 and completed the safety follow up through DLT evaluation period; or 2) who experienced any DLT during the DLT evaluation period. The DLT evaluation period is defined as the first 28 days. The DLT evaluable population will be used to guide dose escalation and to determine the MTD or MAD.
Response Evaluable	All subjects in the All Treated population who have a baseline disease assessment and have at least one post-baseline disease assessment or have progressed or died before the first post-baseline disease
PK Population	Subjects in the All Treated Population who have at least one postdose PK sample obtained and analyzed. The PK population will be used for the PK analysis.

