5.3.3 Study Day, Duration, and Time from Event

The reference date for age calculation is the date of consent form signed as age is an eligibility requirement. The reference date for safety, efficacy and other data analyses is the date of the first dose.

• Study Day – Study Day 1 is defined as the date of the first dose; the day before the first dose is defined as Study Day -1. There is no study day 0. For a given event date, Study Day is calculated relative to the date of first dose of study drug.

```
Study Day = [Event Date – First Dose Date] (in days) + 1 day, where the event date is on or after the first dose date.

Study Day = [Event Date – First Dose Date] (in days), where the event date is before the first dose date.
```

• **Duration (Days)** – A duration is calculated as the stop date minus the start date plus one.

```
Duration (days) = [Stop Date - Start Date] (in days) + 1 day.
```

- **Time since an event** -Time since an event (e.g. time since initial diagnosis) is calculated as the reference date minus the event date. For time since initial diagnosis, the reference date is the first dose of study treatment.
- **Time to an event-** Time to an event (e.g. time to response, PFS, OS) is calculated as the event date minus the reference date+1. For time to response, PFS and OS, the first dose of study treatment is the reference date.

To convert days to months, divide the number of days by 30.4375 (365.24/12) and round to one decimal place.

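### Schedule 2 requires no laboratory test after the Day 22 infusion and inside the 28-day DLT period, and the plan disagrees with itself on whether a Day 29 (C2D1) result counts

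*Protocol*

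**What the plan says.** Protocol 3.4 defines the period: "The determinate period for DLT is the first 28 days of SL-172154 dosing on Schedule 1 or Schedule 2". SAP 4 repeats it: "The DLT evaluation period is defined as the first 28 days". SAP 5.3.3 fixes the day numbering: "Study Day 1 is defined as the date of the first dose".

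Protocol 3.3 also gives the length as 28 days, but ties the end to dosing. The period closes 14 days after the last cycle 1 dose on Schedule 1 "and 7 days after the last dose is administered on Schedule 2".

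In the Schedule 2 assessment table (Protocol 6.2) the cycle 1 visits are Days 1, 2, 3, 8, 15, 16 and 22. The study-day header then runs "22 29 30 36 43 44 50". Day 22 is a dosing day, and footnote o allows no deviation from the dosing days in cycle 1.

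The DLT Evaluable population (Protocol 9.2.1, SAP 4) counts DLTs that occur during the evaluation period. Protocol 9.2.2 and SAP 5.1 take the cohort DLT counts from that population, and those counts enter Table 7 (SAP Table 2). Protocol 3.4 adds that Grade 3 or higher events after the period may be weighed in determining DLT and the RP2D, and that the investigator with the SMC may call other events DLTs.

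**The concern.** Several DLT criteria in 3.4 can be met by a blood result in a patient without symptoms: the transaminase and bilirubin thresholds, Hy's law and Grade 4 thrombocytopenia. Such events are found only if blood is drawn.

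In cycle 1, Schedule 2 differs from Schedule 1 only by the Day 22 infusion, and that infusion has no required laboratory follow-up inside the period. On Schedule 1 the last cycle 1 dose (Day 15) is followed by hematology and chemistry on Days 16 and 22.

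The protocol itself points to laboratory toxicity. Section 1.4.1 lists transaminase elevation, thrombocytopenia and neutropenia for both drug classes. In the monkey GLP study (1.2.4), "Minimally to moderately decreased platelets occurred at ≥10 mg/kg (Days 16 and 23"), that is, one day after the third and fourth weekly doses.

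At stake is the DLT count on which the mTPI-2 rule acts. In a cohort of three, one uncounted event changes the decision.

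**Working it through.** **Inputs**
- DLT period: first 28 days (Protocol 3.4, SAP 4); ends 7 days after the last Schedule 2 dose (Protocol 3.3).
- Day 1 is the first-dose date (SAP 5.3.3).
- Schedule 2 doses in cycle 1: Days 1, 8, 15 and 22. Visits around the end of the period: Day 22, then Day 29 (Protocol 6.2).
- Assessments at intervals of three weeks or less: ±3 days (6.2, footnote b). Infusions from C2D1 on: ±1 day (6.2, footnote o).
- Target DLT rate 30%, Beta(1,1) prior, intervals of width 0.1 (Protocol 9.1).

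**1. The 3.3 figure.** Schedule 2: 22 + 7 = Day 29. Schedule 1: 15 + 14 = Day 29. Counting 28 elapsed days from Day 1: 1 + 28 = Day 29. Section 3.3 is consistent with itself.

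**2. The 3.4 and SAP figure.** Counting Day 1 as the first of 28 days, the last is 1 + 28 − 1 = Day 28. The two rules differ by one day, and that day is the nominal C2D1 visit.

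**3. Scheduled visits on Days 23 to 28 of Schedule 2.** None. Follow-up after the fourth dose within Days 1 to 28 is 28 − 22 = 6 days, with no visit in it.

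**4. Effect of the visit window.** The C2D1 assessment may fall on Days 29 ± 3, that is Days 26 to 32, and the C2D1 infusion on Days 28 to 30.

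| Day of C2D1 blood draw | Counts under 3.3 | Counts under 3.4 and SAP 4 |
|---|---|---|
| 26 to 28 | yes | yes |
| 29 (on time) | yes, if the end day is included | no |
| 30 to 32 | no | no |

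The same abnormality is scored or not according to the day the site draws blood.

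**5. Effect on the decision rule.** Recomputing the mTPI-2 decisions for three subjects gives escalate, stay, de-escalate, and de-escalate with the dose closed, for 0, 1, 2 and 3 DLTs. This matches Table 7. One uncounted event moves 1/3 (stay) to 0/3 (escalate). From Table 7 it also moves 2/6 (stay) to 1/6 (escalate) and 3/9 (stay) to 2/9 (escalate).

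**6. Illustration of size.** Assumptions, none of them from the documents except the 30% target used as the true rate: equal risk at each of four doses; a share *s* of DLTs that show only in the laboratory; every such DLT from dose 4 missed; all others counted.

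- Per-dose risk: p = 1 − (1 − 0.30)^(1/4) = 0.0853.
- Observed rate: 1 − (1 − p)³ × (1 − p(1 − s)), with (1 − p)³ = 0.7653.
- Chance of 0/3, which means escalation: (1 − observed rate)³. With nothing missed it is 0.70³ = 34.3%.

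| s | Observed DLT rate | Chance of 0/3 |
|---|---|---|
| 25% | 28.4% | 36.8% |
| 50% | 26.7% | 39.3% |
| 100% | 23.5% | 44.8% |

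For each *s* this is an upper bound on the bias under the equal-risk assumption, because it supposes that no dose-4 laboratory DLT is caught by an early, unscheduled or ad hoc draw.

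**The case against.** The best defence is that 3.3 already resolves the matter: its arithmetic gives Day 29 on both schedules, so an on-time C2D1 draw lies on the boundary of the period. The visit window allows the draw on Days 26 to 28. Unscheduled laboratory tests are permitted (Protocol 6.9), and ad hoc tests are taken for infusion reactions or cytokine release (6.4.6.1). The SMC reviews all available safety data, not only the Table 7 count. Any fixed period gives the last dose less follow-up, and 3.3 states the 14 and 7 days openly. Section 3.4 also exempts many laboratory findings, such as uncomplicated Grade 3 thrombocytopenia and Grade 3 values that the SMC judges not clinically significant, so the laboratory-only share may be small.

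Much of this stands, and it limits the claim. It does not remove it. The permitted draws are not required ones, 3.4 and SAP 4 do not adopt the 3.3 end day, and SMC review does not change which events the DLT Evaluable definition counts.

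Three stronger readings are not supported:
- **That a laboratory DLT from the fourth dose can never be scored.** Section 3.4 gives a route, though a discretionary one.
- **That the MTDs of the two schedules cannot be compared.** The documents fix no size for the bias, and unequal follow-up after the last dose is a disclosed feature of the design.
- **That the bias is larger because risk sits in the later doses, as with the monkey infusion reactions.** Those were acute clinical signs around dosing. A similar reaction on Day 22 would be seen that day, inside the period, and would trigger ad hoc tests.

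**Conclusion.** The point holds as a gap in required follow-up combined with a conflict in wording. If Schedule 2 is opened, nothing requires a laboratory assessment between the fourth infusion and the end of the period in 3.4 and SAP 4, and the passages disagree on whether the C2D1 pre-dose result counts. Applied as written in 3.4 and the SAP, an abnormality first found on an on-time Day 29 draw is outside the count that drives escalation.

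The bias in the Schedule 2 DLT rate is downward. On the illustrative assumptions it is 1.6 to 6.5 percentage points (30% against 28.4% to 23.5%). The laboratory-only share has no source in the documents, so this shows scale and is not an estimate. That one omitted event can turn a stay into an escalation follows from Table 7 and needs no assumption.

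One item is unverified. The copy read here lacks the hematology and chemistry rows of the Schedule 2 table, so the tests drawn on Days 22 and 29 could not be confirmed. The absence of any visit on Days 23 to 28 does not depend on those rows.

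**What to change.** Reconcile Protocol 3.3, 3.4 and 9.2.1 and SAP 4:
- State one last day of the DLT period.
- State, for both schedules, that the safety laboratory assessment at C2D1, drawn before the C2D1 infusion, is part of the DLT assessment, so that a qualifying abnormality first found there enters the DLT count.
- Confirm that the Schedule 2 table has hematology and chemistry at C2D1.

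If those tests are already scheduled there, no visit or sample is added. The cost is protocol and SAP wording, and a cohort decision that may wait about one day for an on-time draw.

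The change does not recover everything. The monkey platelet falls came the day after dosing, and in the dose-range-finding study platelets were at or moving toward baseline after seven days. A transient fall just after the Day 22 infusion could still be missed by a Day 29 draw.
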